## **1. Sample Size Calculation**

A power calculation based on a study with a similar design investigating the acute benefits of bioactive rich interventions on cognitive function in participants aged 60-80 years, suggests that 30 participants should give sufficient statistical power (Bell and Williams, 2019). To allow for a 10% attrition rate, 33 older adults has been agreed to be recruited.

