## **3. Randomisation Process**

[figure not shown]
The study will be double blinded since neither the participants nor the researcher will know which intervention meal participants are receiving until the study is over. To achieve this, the Latin Square design (4X4) will be followed, by using blocked randomisation with random permuted blocks of four. Another individual not being involved in this study, will assign a code to each of the four intervention meals and these will be kept in a sealed envelope, concealed to the researcher enrolling and assessing participants. On the testing days, the intervention meal soups will be prepared by research personnel not involved in the conduct of the trial.

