## 5. Statistical Plan

The present study aims to investigate the beneficial effects of a meal containing *Pleurotus* oyster mushrooms on neurocognitive performance (objective I) and improvements in the blood serum measures of inflammation and metabolism (objective II) in the acute postprandial period (6-hours post-consumption) in older adults aged 60-80 years old.

Participant sample characteristics will be tabulated using descriptive statistics, using SPSS software. Parametric tests will be used throughout having first confirmed that the test data meet the required assumption of normality. Statistical analyses of the cognitive measures will be performed using SPSS linear mixed modelling (LMM), employing an unstructured covariance matrix to model successive repeat measurements. LMM will be applied to model variance relating to both fixed parameters (eg experimental meal) and random parameters such as differences between participants. The analysis will involve the creation of both unadjusted models and adjusted models by controlling for baseline variables such as sex, fruit and vegetable consumption, physical activity level and health status. Baseline performance will be included as a repeated covariate. Subjects will be included as a random factor.

In the primary analysis of the data in each cognitive task, the Visit Order (Visit), Time after receiving the experimental meal (Time), experimental meal (Intervention) and Time X Intervention interaction will be included as fixed factors in the model. A composite score will be also calculated by the summation of the z scores obtained from each cognitive task, to examine the effect of the intervention meal on the overall cognitive performance.

The data obtained from the metabolic and inflammatory markers will be checked for normality before using parametric statistical tests. The blood serum markers obtained

following the intake of the control meal will be compared with the blood serum markers obtained following the intake of the three mushroom containing soups. The SPSS LMM method will be employed, and the data analysis will be similar to the one performed on the cognitive data without the 'Time' being a fixed factor in the model, since the blood sample will be collected at one time point (6 hours post-intervention). Finally, a correlation will be made for the blood biomarkers and cognitive test scores at the 6-hour post-intervention time point.

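### Does recruiting 33 participants fall short of the stated 10% attrition allowance on 30?

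*Combined protocol and SAP*

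**What the plan says.** Section 1 (Sample Size Calculation) gives three figures. The first is the number needed: the section reports a calculation that "suggests that 30 participants should give sufficient statistical power". The other two, the attrition rate and the recruitment target, come together: "To allow for a 10% attrition rate, 33 older adults has been agreed to be recruited".

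The 30 rests on earlier work, described as "A power calculation based on a study with a similar design". The section does not give the significance level, power, effect size or standard deviation behind it. It also does not say how the 10% was applied, whether it refers to those recruited or to the 30 needed, or how fractions of a person were rounded.

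Section 3 (Randomisation Process) makes the trial a crossover: "the Latin Square design (4X4) will be followed, by using blocked randomisation with random permuted blocks of four". Every participant is meant to receive all four meals, so no between-arm allocation ratio enters the step from 30 to 33. Section 5 (Statistical Plan) analyses the cognitive outcomes, and in a similar way the blood markers, with a linear mixed model.

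**The concern.** Attrition is usually understood as the share of recruited participants who are lost. To keep n participants after losing a fraction d, one recruits n/(1 - d). Multiplying by (1 + d) instead is a familiar mistake, because it takes the percentage of the wrong base and gives too small a target. Here 30 x 1.10 is exactly 33, so the mistake seems to be in plain view, and taking 10% off 33 gives 29.7, below the 30 the plan relies on.

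If that were a real error, the trial would be planned to finish slightly under its own required number, and the stated rate and the stated target would contradict each other. It is also the only step in the sample-size section that a reader can check, since the inputs to the 30 are not given.

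**Working it through.** **Inputs**, all from Section 1: participants needed n = 30; attrition rate d = 10%; recruitment target 33.

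**1. Reproducing the plan's figure.** Two routes are plausible.

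- Multiplying: n x (1 + d) = 30 x 1.10 = 33.0, which is 33 exactly.
- Dividing: n/(1 - d) = 30/0.90 = 33.33, which is 33 to the nearest whole person and 34 if always rounded up.

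Both routes can give 33. The document does not show which was used, so the match with 30 x 1.10 is no evidence that the wrong formula was applied.

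**2. What 33 covers in whole people.** The margin is 33 - 30 = 3 withdrawals.

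| Withdrawals | Share of 33 recruited | Remaining |
|---|---|---|
| 3 | 3/33 = 9.1% | 30 |
| 4 | 4/33 = 12.1% | 29 |

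No whole number of withdrawals from 33 is exactly 10%. The expected number at 10% is 33 x 0.10 = 3.3. The nearest whole number is 3, which leaves exactly 30. If the 10% was meant relative to the number needed, then 3/30 = 10% exactly. On either base, the stated rate and the stated target are compatible.

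**3. The apparent shortfall.** In expectation, 33 x 0.90 = 29.7, and 30 - 29.7 = 0.3 of a participant. With 34 recruited, 34 x 0.90 = 30.6. The two targets differ by one person, and their expected completers lie either side of 30.

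**4. What it costs in precision.** Assume that standard errors scale with 1/sqrt(n) and, as a worst case, that a withdrawn participant contributes no data. No significance level, power or standard deviation is needed.

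- At 29.7 completers: sqrt(30/29.7) = 1.005, so standard errors are 0.5% wider than at 30.
- At 29 completers: sqrt(30/29) = 1.017, so 1.7% wider.

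A mixed model can use the visits that a participant completed before leaving. To the extent that those visits are kept in the analysis, the loss is smaller than this.

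**The case for a change.** The strongest opposing case does not depend on how 33 was reached. On the ordinary meaning of an attrition rate, 33 less 10% is 29.7 by any route, and rounding 33.3 down leaves the target slightly short. The usual cautious practice is to round up, which gives 34. If each participant independently has a 10% chance of withdrawing (an assumption the plan does not make), the probability of keeping at least 30 is 0.58 with 33 recruited and 0.75 with 34, which is not a trivial difference. Stating that 33 covers 3 withdrawals, about 9%, would be true under every convention and would cost one sentence.

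The sums are right, and 34 would have been a defensible target. The rest does not make this an error. The two probabilities matter only if 30 is a threshold below which the trial fails. Section 1 does not present it that way: it says only that 30 should be sufficient, and gives no inputs that would make 29 inadequate. Step 4 of the working shows how little changes on crossing from 30 to 29.

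The rewording is not an improvement either. Ten percent is a round planning rate for expected withdrawals. Replacing it with about 9% would put a figure back-calculated from the target in its place, with nothing to suggest that 9% is what the trial team expects. Recruitment, analysis and interpretation would all stay as they are. A note of the formula and rounding rule would be tidy, but its absence does not make 33 wrong.

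**Conclusion.** The concern does not hold. The target of 33 follows from the plan's own 30 and 10% both by multiplication and by the standard division rounded to the nearest person, and 3 withdrawals, the whole number closest to 10% of 33, leave exactly 30. What remains is a choice between rounding to the nearest person and rounding up. It is worth one participant in the target and 0.3 of a participant in expected completers. The worst-case effect on standard errors is 0.5% at 29.7 completers and 1.7% at 29.

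This rests on taking the 30 as given, since its inputs are not stated and it cannot be recalculated, and on standard errors scaling with 1/sqrt(n). It does not settle whether 30 is itself adequate, which is a separate question from the attrition step.

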## **2. Recruitment and Screening**

Participants will be initially recruited using opportunity sampling. The study will be advertised via email and posters will be placed around public areas (eg university area, sports hall, library, churches, GP practices). Furthermore, participants will be recruited from the Age UK Berkshire and the local community and if needed from the university of Reading research ageing panel.

Before interested participants are enrolled in our study, they will be invited to attend a screening and familiarization session to our unit, to determine if they meet the eligibility criteria and they will be given an opportunity to become familiar with the cognitive task battery to reduce the influence of practice effects. Participants will be compensated with £200 for completing all study visits.

## **3. Randomisation Process**

[figure not shown]
The study will be double blinded since neither the participants nor the researcher will know which intervention meal participants are receiving until the study is over. To achieve this, the Latin Square design (4X4) will be followed, by using blocked randomisation with random permuted blocks of four. Another individual not being involved in this study, will assign a code to each of the four intervention meals and these will be kept in a sealed envelope, concealed to the researcher enrolling and assessing participants. On the testing days, the intervention meal soups will be prepared by research personnel not involved in the conduct of the trial.

## **4. OYSACO study Protocol**

During this study, participants will attend the University of Reading, Psychology department on five separate occasions, with a week interval between each visit.

In the pre-screening phase, the participants interested in our study will be sent a link to REDCap containing online versions of a Health and Lifestyle Questionnaire and the Epic Norfolk Food Frequency Questionnaire (FFQ). Then, participants, will be contacted to attend a 2-hour screening session at our department, during which the participant's weight, height and blood pressure will be checked, along with a finger-prick, to ensure that the participants are not anaemic. Furthermore, participants will complete the Raven's Progressive Matrices (RPM) measure of fluid intelligence and will perform the cognitive battery tasks twice to control for practice effects in the run up to the test session days.

One week after the screening visit, each participant will attend a further four test sessions, each separated by a week, where they will receive a different dose of freeze-dried oyster mushrooms or a control soup. Participants will be asked to follow a low fibre and flavonoid diet for 48 hours in advance of testing and these four testing days participants have to remain to our unit from 08:00 a.m.- 16:00 p.m. **Figure 1** summarises the OYSACO testing protocol.

**Figure 1:** Study design of the 4-arm OYSACO RCT, investigating the dose-response effects of an acute diet containing ergothioneine-rich *Pleurotus* mushrooms on the cognitive, metabolic and inflammatory function in healthy older adults.

(\*). For the soup interventions, the *Pleurotus* mushrooms will be in a powdered form at varying doses (equivalent to 0.5 (soup 1), 1 (soup 2) and 2 (soup 3) mushroom servings (with 1 serving~8g powdered mushrooms)).

## 5. Statistical Plan

The present study aims to investigate the beneficial effects of a meal containing *Pleurotus* oyster mushrooms on neurocognitive performance (objective I) and improvements in the blood serum measures of inflammation and metabolism (objective II) in the acute postprandial period (6-hours post-consumption) in older adults aged 60-80 years old.

Participant sample characteristics will be tabulated using descriptive statistics, using SPSS software. Parametric tests will be used throughout having first confirmed that the test data meet the required assumption of normality. Statistical analyses of the cognitive measures will be performed using SPSS linear mixed modelling (LMM), employing an unstructured covariance matrix to model successive repeat measurements. LMM will be applied to model variance relating to both fixed parameters (eg experimental meal) and random parameters such as differences between participants. The analysis will involve the creation of both unadjusted models and adjusted models by controlling for baseline variables such as sex, fruit and vegetable consumption, physical activity level and health status. Baseline performance will be included as a repeated covariate. Subjects will be included as a random factor.

In the primary analysis of the data in each cognitive task, the Visit Order (Visit), Time after receiving the experimental meal (Time), experimental meal (Intervention) and Time X Intervention interaction will be included as fixed factors in the model. A composite score will be also calculated by the summation of the z scores obtained from each cognitive task, to examine the effect of the intervention meal on the overall cognitive performance.

The data obtained from the metabolic and inflammatory markers will be checked for normality before using parametric statistical tests. The blood serum markers obtained

following the intake of the control meal will be compared with the blood serum markers obtained following the intake of the three mushroom containing soups. The SPSS LMM method will be employed, and the data analysis will be similar to the one performed on the cognitive data without the 'Time' being a fixed factor in the model, since the blood sample will be collected at one time point (6 hours post-intervention). Finally, a correlation will be made for the blood biomarkers and cognitive test scores at the 6-hour post-intervention time point.

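### Does leaving the index of the unstructured covariance matrix unstated make the section 5 mixed model unreliable with 30 to 33 participants?

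*Combined protocol and SAP*

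**What the plan says.** The combined protocol and SAP describes the cognitive analysis in section 5. The model is fitted in SPSS "employing an unstructured covariance matrix to model successive repeat measurements". It also covers "random parameters such as differences between participants", and the section adds: "Subjects will be included as a random factor". Visit order is a fixed factor, and "Time after receiving the experimental meal (Time), experimental meal (Intervention) and Time X Intervention interaction will be included as fixed factors". On the pre-meal score it says: "Baseline performance will be included as a repeated covariate".

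For the blood markers, "the data analysis will be similar to the one performed on the cognitive data", except that Time is removed because each visit yields a single 6-hour sample.

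Section 4 gives four weekly test sessions after screening. Section 3 gives a 4x4 Latin square. Section 1 gives 30 participants, raised to 33 for attrition.

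Three things are not stated: the index of the unstructured matrix, the block within which it applies (participant or participant-visit), and the degrees-of-freedom method.

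**The concern.** Each participant is measured repeatedly on two axes: over time within a session, and over four sessions. The phrase about successive measurements could refer to either axis or to both. If the matrix spans every visit-by-time cell of a participant, it has more free parameters than there are participants. The estimated standard errors are then too small.

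This is the primary model for every cognitive task. If the plan led analysts to that form, meal effects would be declared too often, and a small-sample correction would repair only part of the excess. The marker model is defined by reference to the cognitive one, so it inherits the same question.

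**Working it through.** **Inputs from the document.** Four test visits (section 4). 30 participants and 10% attrition (section 1): 30 x 1.10 = 33, which reproduces the stated target. So n runs from 30 to 33.

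**Input that must be assumed.** T is the number of post-meal cognitive time points. Time is a factor with an interaction and baseline is a covariate, so T is at least 2. The study-design figure that may give T is not readable, so T = 2 and T = 3 are used.

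**Parameter counts.** An unstructured matrix of dimension p has p(p+1)/2 parameters.

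- Within participant-visit, p = T. T = 2: 2 x 3/2 = 3. T = 3: 3 x 4/2 = 6. The participant intercept adds one, giving 4 and 7. They are estimated from 4 x 30 = 120 to 4 x 33 = 132 blocks.
- Per participant over visit by time, p = 4T. T = 2: 8 x 9/2 = 36. T = 3: 12 x 13/2 = 78. The blocks number only 30 to 33.

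**Does each form accept the stated random participant factor?** A participant intercept adds one constant to every element of the participant's covariance matrix. A full visit-by-time matrix can already absorb that constant, so the two together are not identifiable: 37 parameters with rank 36 at T = 2, and 79 with rank 78 at T = 3. Within participant-visit, the intercept is what links the visits, and all parameters are identifiable (4 of 4, 7 of 7).

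**Type I error.** Null simulation by REML with complete data and n = 33, comparing top dose with control averaged over time. There were three assumed sets of variances (participant, visit, residual): (1, 0.25, 0.49), (0.5, 0.5, 0.5) and (1, 0, 1). The meal x time row uses the first and third sets only. Monte Carlo error is 0.3-0.7 points at 5% and about 1.2 points at 20%.

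| Structure | T = 2 | T = 3 |
|---|---|---|
| Within visit + participant intercept (Satterthwaite and Kenward-Roger agree) | 4.7-5.1% | 4.0-5.2% |
| Participant-level, visit x time, Satterthwaite | 12.1-12.7% | 17.2-19.7% |
| Participant-level, visit x time, Kenward-Roger | 6.3-7.0% | 7.9-10.2% |
| Participant-level, meal x time | 5.0-5.1% | 4.4-5.4% |

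A second simulation used assumed SDs of 0.8, 0.4 and 0.5, n = 30 and 33, approximate degrees of freedom and no small-sample correction. The visit-by-time form gave 12.2-12.5% at T = 2 and 15.5-18.4% at T = 3. The within-visit form gave 4.7-6.5% for T = 2 to 4, with model SE at 0.97-1.02 of the true SE.

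**What drives the inflation.** The meal-by-time matrix has the same 36 or 78 parameters at the same n, yet the contrast stays near 5%. Size alone is therefore not the cause. In a Latin square a meal falls at different visits in different sequences. With a visit index, the weights given to the sequences depend on the poorly estimated matrix. With a meal index, apart from the visit and baseline adjustments, each participant contributes the same contrast of cells.

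**Time x Intervention F test.** The within-visit form gives 4.4-5.2% (T = 2) and 4.7-5.6% (T = 3) with Kenward-Roger. The visit-by-time form gives 8.3-8.5% and 16.3-18.0%.

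**Markers** (one value per visit, first variance set, n = 33). With Time removed and participants random, the direct analogue is a random intercept with one residual variance, which gives 5.1%. A 4x4 matrix by visit has 4 x 5/2 = 10 parameters, and adding the intercept makes 11 with rank 10. Without the intercept it gives 8.3%, or 5.7% with Kenward-Roger.

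**The case for a change.** The best case for a change is that the identifiability argument is only a hint. No sentence confines the matrix to a visit, and a plan should not need its reader to deduce the block from a rank calculation. An analyst could put every cell into one participant-level matrix, drop the intercept and report the result. Kenward-Roger, which the plan does not name, would still leave 6-10% for the contrast. Precision would also suffer: the contrast variance is 23-36% larger at T = 2 and 49-62% larger at T = 3. Two sentences would close the gap and prevent the structure from being chosen after the results are seen.

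Part of this stands. The index, block and degrees-of-freedom method are indeed missing, and the bad form is bad under the variances assumed. But reaching it means discarding a component the plan states outright. The missing degrees-of-freedom method does no harm to the contrast on the coherent reading, where the two usual methods gave the same rates. The precision penalty was measured under variances that fit the within-visit model exactly, so it is not a general figure.

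Nor is the within-visit model immune to every departure. If the top-dose variance is 1.5, 2 or 3 times that of the other meals, its contrast error becomes 6.0, 6.7 and 8.6% at T = 2, and 7.1, 6.4 and 7.7% at T = 3. Writing down the index would not alter that, and the visit-by-time form does worse at ratio 2: 13.4% (Kenward-Roger 8.3%) at T = 2 and 21.3% (11.4%) at T = 3.

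**Conclusion.** The concern identifies a real omission of detail, but no change to the plan follows. The stated components fit together in one natural way: a random participant intercept with an unstructured matrix over the successive times within each participant-visit. That model has 4 or 7 covariance parameters at T = 2 or 3, draws on 120-132 blocks, and holds 4.0-5.2% for a single meal contrast in the main simulation. Rates of 12-20% (6-10% with Kenward-Roger) belong to a different model, which makes the stated participant factor redundant. For the markers, the direct analogue holds 5.1%, and even the unfavourable form is 5.7% with Kenward-Roger.

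This is a gap that an analyst fills sensibly when setting up the model. Spelling it out would record the analysis the text already implies. The parameter counts depend only on T. The error rates also rest on assumed variances, complete data and, for the figures near 5%, equal variance across meals.

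### A single repeated baseline slope with random subjects mixes between-person and within-person signals; splitting it can tighten the meal main effect and single-time meal contrasts at almost no cost

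*Combined protocol and SAP*

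**What the plan says.** Section 5 (Statistical Plan) analyses each cognitive task with an SPSS linear mixed model, "employing an unstructured covariance matrix to model successive repeat measurements". The fixed effects are visit order, time since the meal, "experimental meal (Intervention) and Time X Intervention interaction will be included as fixed factors in the model". Baseline and the subject effect are handled in two short sentences: "Baseline performance will be included as a repeated covariate. Subjects will be included as a random factor".

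On design, section 3 states that "the Latin Square design (4X4) will be followed, by using blocked randomisation with random permuted blocks of four", and section 4 that "each participant will attend a further four test sessions, each separated by a week". Every participant therefore receives all four meals.

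The text does not say which score is the baseline, how many post-meal test times there are, or whether the unstructured matrix covers times within a visit or all visits. The schedule figure is not shown in the text available. The natural reading of a repeated covariate is one pre-meal score per test visit, and that reading is used here.

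**The concern.** A baseline measured at each visit carries two kinds of information. One is the participant's stable level, which predicts the post-meal score almost one for one. The other is how far that day's score departs from the participant's own average. Much of that departure is measurement noise, so its slope is usually smaller.

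A single covariate allows only one slope. With subjects random, that slope is a weighted mix of the two. Meal contrasts compare visits within the same person, so only the within-person slope helps them. A larger slope adds baseline noise to the contrast instead of removing it. The adjusted models' other covariates (sex, diet, activity, health status) are described as baseline characteristics and do not separate the two slopes.

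The stake is the width of the intervals for the overall meal effect and for a meal contrast at, say, 6 hours, in a trial of about 30 evaluable people. Time X Intervention contrasts are not affected with complete data: a visit's baseline is the same at all its post-meal times and cancels.

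**Working it through.** **The plan's own figure.** The plan gives no figure for this point. Its sample size (section 1) is 30 evaluable plus 10% attrition: 30 × 1.10 = 33, as stated. The 30 cannot be rebuilt, because no alpha, power, effect size or SD is given. It is used below as n.

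**Inputs.** From the documents: n = 30, four visits, four meals, random subject, and fixed visit, time, meal and time-by-meal. Assumed, because the documents are silent: variance components for subject (S), visit within subject (V) and single occasion (E), with S + V + E = 1, and K post-meal times. ICC = S. The share of within-person variance common to a visit's baseline and post-meal scores is V/(V + E).

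**Formulas.** Baseline = subject + visit + own error; each outcome = subject + visit + own error.
- Within-person slope: V/(V + E).
- Between-person slope (means over four visits): (S + V/4) / (S + (V + E)/4).
- Within-person residual variance of the mean of K outcomes at slope b: R_K(b) = V + E/K − 2bV + b²(V + E).
- Variance of a two-meal contrast: about 2R/n.

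**Central case: S = 0.70, V = 0.10, E = 0.20** (ICC 0.7, one third shared).
- Within-person slope: 0.10/0.30 = 0.33. Between-person slope: 0.725/0.775 = 0.94.
- One time: the fitted single slope is 0.74. R₁(0.33) = 0.300 − 0.067 + 0.033 = 0.267. R₁(0.74) = 0.300 − 0.148 + 0.164 = 0.316. The ratio is 1.19; REML simulation gave 1.17 to 1.19. With no baseline R₁(0) = 0.300, so here the single slope does worse than no adjustment.
- Mean of three times: the fitted single slope is about 0.65. R₃(0.33) = 0.167 − 0.067 + 0.033 = 0.133. R₃(0.65) = 0.167 − 0.130 + 0.127 = 0.163 (unrounded 0.1634/0.1333). The ratio is 1.23. SEs: √(2 × 0.133/30) = 0.094 and √(2 × 0.163/30) = 0.104. Simulation (1500 runs) gave 0.0960 and 0.1066, again a ratio of 1.23.
- One of three times at the same slope: 0.297/0.267 = 1.11.

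**Range.** REML simulation with n = 30, 4x4 Williams sequences and complete data; ICC 0.5, 0.6, 0.7, 0.8 crossed with shared fraction 0, 0.2, 0.33, 0.5, 0.7 (20 scenarios per row). Model-variance ratio, single over split slope, top dose versus control:

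| Structure | Ratio |
|---|---|
| One time | 1.01-1.40 |
| Two times, random intercept only | 1.01-1.10 |
| Two times plus visit-level term | 1.03-1.40 |
| Three times, random intercept only | 1.01-1.04 |
| Three times plus visit-level term | 1.04-1.42 |
| Three times, unstructured within visit, averaged | 1.05-1.40 |
| Three times, unstructured within visit, last time | 1.01-1.20 |
| Three times, unstructured, Time X Intervention | 1.00 in all 20 |

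The first five rows used 600 replicates per scenario, and the empirical variances agreed (1.00-1.58). The unstructured rows used 120 replicates, so their empirical ratios are noisy (0.97-1.37 averaged, 0.93-1.19 last time). On a wider grid (ICC 0.3-0.8, 0-90% shared, subject-plus-visit structure) the model-variance ratio ran from 1.00 to 1.43.

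**Meaning in the central case, three times.** Equivalent sample size is 30/ratio: 30/1.23 = 24 (averaged, unstructured), 30/1.11 = 27 (last time, unstructured), 30/1.02 = 29 (averaged, random intercept only). If the split model had 80% power at two-sided 5%, a ratio of 1.23 gives (1.960 + 0.842)/√1.23 − 1.960 = 0.566, or about 71% power.

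**Validity.** In simulation both models were unbiased, with type I error between 0.041 and 0.058.

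**Cost of splitting.** Where the two slopes were nearly or exactly equal, the split model's SE was at most 0.3% higher than the single slope's. Against no baseline at all, its model variance was at most about 1.5% higher.

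**The case against.** The strongest case against is that the planned analysis is valid and the gain may be negligible.

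- **Assumed variances.** Nothing in the documents says where this trial lies on the grid. With one post-meal time the ratio was only 1.03 at ICC 0.3 with one third shared, 1.01 at ICC 0.3 with 70% shared, and 1.02 at ICC 0.7 with 90% shared. If the slopes coincide there is no gain. This stands, and is why the size is given as a range.
- **Undefined covariance structure.** With three times, the averaged contrast loses 5-40% under an unstructured within-visit matrix but 1-4% under a random intercept only. The plan names an unstructured matrix but not its extent, so the larger figures rest on one reading. This stands.
- **Undefined baseline.** If the screening score were meant, there would be no within-person part and the point would fall. A single screening value would not be a repeated covariate, so this is the less natural reading, but the plan should settle it.
- **An unaffected test.** Time X Intervention does not change, and the plan does not say whether it or the meal main effect decides. This limits the point without removing it, since the meal effect is also in the model.
- **Single slope often helps.** For the averaged contrast under the unstructured structure, single slope over no baseline ran from 0.41 to 1.27 and was below 1 in 12 of 20 scenarios. In the other 8 the planned adjustment did worse than none.
- **Dropout.** The ranges assume complete data, while 10% attrition is expected. A check with six dropouts (one time, ICC 0.7, one third shared) gave 1.17 against 1.19 with complete data, so dropout made little difference there.

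**Conclusion.** The point holds as an optional gain in efficiency, not as an error. A single visit-level baseline slope with random subjects can widen the intervals for the meal main effect and single-time meal contrasts. It does not bias them, and it leaves Time X Intervention unchanged with complete data.

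For ICC 0.5-0.8 and 0-70% shared within-person variance, the extra variance lies between about 1% and 40%, depending mainly on the covariance structure and the number of post-meal times. In the central case it is 23% (averaged, unstructured), 11% (last time, unstructured) or 2% (averaged, random intercept only). All of this assumes a pre-meal baseline at each test visit and variance components that the documents do not give. Confidence in the direction is good; confidence in the size for this trial is moderate at best.

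**What to change.** First, state in section 5 that the baseline is the pre-meal score of each test visit. Then replace the single repeated baseline covariate with two:

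1. the participant's mean baseline over the test visits attended;
2. the visit's baseline minus that mean.

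Entering the visit's baseline together with the participant's mean gives the same fit. Visit, Time, Intervention, Time X Intervention and the random subject stay as planned.

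The cost is a sentence or two of SAP wording, one derived variable and one degree of freedom. No new data, visits or tests are needed.
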